**Eligibility**

- Inclusion Criteria: Definite diagnosis of myofascial pain with a referral, based on the DC/TMD criteria, presence of the myofascial pain for at least six months; the presence of one or more trigger point in the unilateral or bilateral masseter muscle, no history of any invasive procedures in the related masseter muscle in last two years;
- Exclusion criteria: Factors that can cause pain in the orofacial region other than MTPs (decayed tooth, TMJ internal disorder, etc.), presence of any muscle disorders or neuropathy (e.g. fibromyalgia), patients with a history of hypersensitivity to local anesthetics.

Patients were grouped according to the treatment they received: Masseteric nerve block (MNB), TrP injections with local anesthetic (LA) and dry-needling (DN). Localization of the MTPs was based on the clinician's sense and patients' expressions of pain. Local twitch response was not observable in all cases. This procedure was completed by using digital palpation. Clinical examiner's palpation was calibrated using a pressure algometer (1.5 Kg).

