**Outcome measures**

The Rate of Pain on Function (PoF) assessed by Numerical pain Scale (NRS): Patients rated their pain on function (pain during chewing or speaking etc.) on a Numeric Rating Scale (NRS) (0–10 where 0 is no pain and 10 is the worst pain imaginable)

The Rate of Pain Intensity on Palpation (PoP): Patients rated their pain intensity on masseter muscle by a 4-point Likert-type scale (0 = no pain, 3 = as worst pain imaginable) while a calibrated examiner palpating their masseter muscle.

The measurement of pain-free maximum mouth opening (MMO) in millimeters.: Pain-free MMO was measured as the distance between the incisal edges of the upper and lower incisors while patient's mouth is open as possible without any assistance and without pain in masseter muscle. Three measurements were performed, and their average is recorded.

The patients were assessed before the injections (T0), and at one week (T1), 4 weeks (T2), and 12 weeks (T3) after the injections. Patient's pain on palpation, pain on function and maximum mouth opening values were reexamined and recorded on follow-up appointments. Treatment protocol and the outcome measures were recorded in the patient's form.

Statistical Analysis Plan: Descriptive statistics of variables were presented as mean  $\pm$  standard deviation for continuous variables and n (%) for categorical variables in statistical analysis. IBM SPSS 22 was used to analyze the data (IBM SPSS Statistics for Windows, Version 22.0. Armonk, NY: IBM Corp.). Pearson chi-square test was used in the analysis of categorical variables. One-way ANOVA was used in the analysis of discontinuous variables (such as % difference Baseline-T1). Bonferroni test was used as post hoc test after ANOVA. Repeated Measures ANOVA test was used when testing group differences for repeated measurements. Bonferroni correction was used in multiple comparisons when determining the differences between the groups at each time point. The statistical significance level was accepted as  $p < 0.05$ .

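### Neither planned between-arm comparison adjusts for the T0 score, and percent change from baseline is a poor substitute for that adjustment

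*Combined protocol and SAP*

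**What the plan says.** The Statistical Analysis Plan paragraph, under Outcome measures, describes two ways of comparing the arms.

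- For derived variables: "One-way ANOVA was used in the analysis of discontinuous variables (such as % difference Baseline-T1", followed by a Bonferroni post hoc test.
- For the serial scores: "Repeated Measures ANOVA test was used when testing group differences for repeated measurements". It adds: "Bonferroni correction was used in multiple comparisons when determining the differences between the groups at each time point".

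No covariate is named in either, and neither is called primary. The text does not list which outcomes are turned into percent change, and does not say whether T0 is one of the time points in the repeated-measures model.

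The baseline score is available: "The patients were assessed before the injections (T0), and at one week (T1), 4 weeks (T2), and 12 weeks (T3) after the injections". PoF is scored "0–10 where 0 is no pain and 10 is the worst pain imaginable" and PoP on a "4-point Likert-type scale (0 = no pain, 3 = as worst pain imaginable", so zero is a legal value on both. Eligibility asks for a diagnosis, at least one trigger point and "presence of the myofascial pain for at least six months". It sets no minimum score at T0, and no rule covers a T0 of zero.

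**The concern.** Percent change looks like a baseline adjustment but in general is not one. Dividing by T0 removes dependence on T0 only if the expected follow-up score is strictly proportional to it. Otherwise an arm that starts higher or lower by chance carries that difference into its mean percent change. The per-visit comparisons attached to the Repeated Measures ANOVA have the same gap, because as written they compare arms without conditioning on T0.

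Division by a short bounded score also gives the same absolute improvement very different weights, so patients with low T0 can dominate both the mean and the variance.

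At stake are the precision of the arm contrasts and their bias under the imbalance that happens to occur. With 15 patients per arm, neither can be assumed small.

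**Working it through.** **The plan's own figure.** The Sample size section gives 45 patients (15 per arm) at power 0.80 and alpha 0.05, but no endpoint, effect, SD or test, so it cannot be reproduced. Working backwards, a three-group one-way ANOVA with N = 45 (df 2, 42) has 80% power at Cohen's f = 0.48. That f serves as a reference below. All SDs, means, correlations (ρ) and effects that follow are assumptions.

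**1. Unequal weighting (no assumptions).** A 1-point NRS fall is 1/8 = 12.5% from 8 and 1/2 = 50% from 2. If percent change is also applied to PoP, one point is 33%, 50% or 100% from 3, 2 or 1.

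**2. Zero baseline.** For a rounded normal PoF with mean 6 and SD 1.8, P(score 0) = P(Z < (0.5 − 6)/1.8) = P(Z < −3.06), about 0.1%. The chance of at least one zero among 45 is then 1 − (1 − 0.001)^45, about 5%. For mean/SD of 7/1.5, 6/2 and 5/2 that chance is 0.03%, 13% and 43%.

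**3. Chance imbalance.** The difference in mean T0 between two arms of 15 has standard error √(2/15) = 0.37 SD. In simulation, the median gap between the highest and lowest of three arm means is 0.41 SD, and it exceeds 0.5 SD in 36% of trials.

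**4. How imbalance reaches the estimate.** Write the expected follow-up score as a + b·T0, with b = ρ × (follow-up SD)/(T0 SD). Expected percent fall is then 100 × (1 − b − a/T0), which is free of T0 only if a = 0.

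- T0 6/2, follow-up 4/2, ρ = 0.5: b = 0.5 and a = 4 − 0.5 × 6 = 1. Simulated with no treatment effect, a gap of 0.5 / 0.75 / 1.0 SD between the extreme arms gives a spurious difference of 4.8 / 7.4 / 10.1 percentage points.
- T0 6/1.8, follow-up 3.5/2, ρ = 0.5: b = 0.5 × 2/1.8 = 0.556 and a = 3.5 − 0.556 × 6 = 0.17, so dependence on T0 nearly vanishes. At ρ = 0.3, a = 3.5 − 0.333 × 6 = 1.5. At ρ = 0.7, a = 3.5 − 0.778 × 6 = −1.17. The direction of the bias therefore changes with ρ.
- An unadjusted comparison of raw follow-up scores in the first setting carries b × gap. For a 0.5 SD gap that is 0.5 × (0.5 × 2) = 0.5 NRS points.

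**5. Type I error.** With no effect, percent-change ANOVA rejected in 4.1% to 4.9% of trials across nine settings. Conditional on gaps of 0.5 / 0.75 / 1.0 SD in the first setting of step 4, it rejected in 4.4% / 5.3% / 5.7%, against 4.9% for ANCOVA.

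**6. Power, additive effect.** T0 6/1.8, follow-up mean 3.5, SD 2, one arm better by 2 points at T3, 20,000 simulated trials per setting, scores rounded to 0–10:

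| ρ | Percent-change ANOVA | ANCOVA on T0 | Gain (points) |
|---|---|---|---|
| 0.3 | 0.71 | 0.79 | 8 |
| 0.5 | 0.82 | 0.85 | 3 |
| 0.7 | 0.91 | 0.95 | 4 |

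In nine other additive settings (T0 7/1.5, 6/2 and 5/2; follow-up SD 2; arm effects 0, 1.2 and 2.4 points; the same three ρ), ANCOVA was ahead in all, by 0.8 to 16.8 points.

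**7. Power, purely proportional effect.** With reductions of 30%, 45% and 60% in the three arms:

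| T0 mean/SD | Percent-change ANOVA | ANCOVA on T0 | Difference (points) |
|---|---|---|---|
| 7/1.5 | 80.0% | 77.6% | −2.4 |
| 6/2 | 78.8% | 74.5% | −4.3 |
| 5/2 | 76.4% | 72.9% | −3.5 |

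**8. T0 as a repeated outcome instead of a covariate.** With only T0 and one follow-up, the group-by-time test is an ANOVA on raw change. At f = 0.48 and equal SDs, the noncentrality N·f² is multiplied by 1/(2(1 − ρ)) for change and by 1/(1 − ρ²) for ANCOVA. Power at ρ = 0.3 / 0.5 / 0.7 is 64.8% / 80.0% / 95.7% for change and 83.7% / 90.4% / 98.0% for ANCOVA. This is indicative only, since the plan has four visits.

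**The case against.** The strongest reply is that percent change is only an example of what the one-way ANOVA is used for, and that the arms are also compared on the repeated measurements. That is right, and a reader who took percent change to be the only between-arm test would be misreading the plan. If T0 is a time point in the repeated-measures model, the group-by-time test uses the baseline without dividing by it and keeps a patient who scores zero at T0. This narrows the point but does not remove it. T0 would then enter as an outcome, not a covariate (step 8), and the per-visit comparisons remain unadjusted as written.

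Three further objections stand:

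- **Power.** A reader might infer that percent change always loses power. The documents give no SD, correlation or shape of effect, and step 7 shows a small reversal under proportional effects.
- **Validity.** A reader might infer from the imbalance figures that the test is invalid. Randomisation makes the imbalance chance, the F-test allows for it, and the rejection rate stays close to 5%. The cost is precision and conditional bias.
- **Zero baseline.** Patients enter with established masseter pain, so a zero PoF should be rare: at most about 1.2% per patient in the settings of step 2. It is not a practical issue for MMO. Nor do the documents say that such a patient would be excluded; they are silent.

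Calling percent change a discontinuous variable looks like a slip of wording and has no analytic consequence.

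**Conclusion.** The point holds as a recommended improvement. No planned arm comparison conditions on T0, although T0 is collected for every outcome. The unequal weighting of percent change is arithmetic and needs no assumption. The bias from chance imbalance is real but conditional: 4.8 to 10.1 percentage points for gaps of 0.5 to 1.0 SD in one assumed setting, and close to nil in another. The power gain from ANCOVA is about 3 to 8 points in the rounded additive setting (0.8 to 16.8 across the other additive settings), and it becomes a loss of about 2 to 4 points if effects are purely proportional.

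The documents do not support a claim that the planned tests are invalid, that they inflate false positives materially, or that zero baselines are likely to remove many patients.

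**What to change.** Revise both analysis sentences, since changing only the percent-change sentence would leave the per-visit comparisons unadjusted. Suggested wording:

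*PoF and MMO at T1, T2 and T3 are compared between arms on the observed score, by ANCOVA at each follow-up [or: by a repeated-measures or mixed model over T1–T3 with arm, time and arm-by-time], with the T0 score as covariate. Bonferroni-corrected pairwise comparisons are made on the adjusted means and reported with 95% confidence intervals. PoP (0–3) is compared by an ordinal method adjusted for the T0 score. Percent change is descriptive only, and the number of patients with T0 = 0, for whom it has no value, is stated.*

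The sponsor should choose one of the two PoF/MMO options in advance. If the data have already been analysed, the adjusted analysis should be labelled as added later.

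The cost is wording and a little more analysis work, with no new data. The possible downside is the small loss of power if effects are in truth proportional.

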**Study Design:**

This is a 3-armed randomized, parallel, controlled, interventional clinical study enrolling 45 patients with myofascial pain originated from masseter muscle.

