**Sample size**

The sample size was calculated using IBM SPSS 22 (IBM SPSS Statistics for Windows, Version 22.0. Armonk, NY: IBM Corp.). Based on a power of 0.80 and an alpha value of 0.05, the sample size was calculated to be a total of 45 subjects with 15 in each group.

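### With exactly three arms, Bonferroni after the one-way ANOVA is valid but gives up pairwise power that an omnibus-gated closed test would keep at the same 5% familywise error

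*Combined protocol and SAP*

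**What the plan says.** The Study Design section states: "This is a 3-armed randomized, parallel, controlled, interventional clinical study enrolling 45 patients". The Eligibility section names the arms as masseteric nerve block, trigger-point injection of local anaesthetic, and dry needling, which gives three pairwise comparisons. Under Sample size, "the sample size was calculated to be a total of 45 subjects with 15 in each group".

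The Statistical Analysis Plan, at the end of Outcome measures, uses Bonferroni in two places:

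- **After one-way ANOVA.** "One-way ANOVA was used in the analysis of discontinuous variables (such as % difference Baseline-T1"), and then "Bonferroni test was used as post hoc test after ANOVA".
- **After repeated measures ANOVA.** "Bonferroni correction was used in multiple comparisons when determining the differences between the groups at each time point".

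The significance level is 0.05. The plan does not say why Bonferroni was chosen and mentions no stepwise or closed procedure. That pairs are examined only after a significant ANOVA is implied by the term post hoc; it is not stated.

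**The concern.** In the one-way ANOVA sentence, a pair has to clear two hurdles: the omnibus F test at 0.05, then its own test at 0.0167. With three arms the first hurdle does most of the work. If any two pairs are equal, so is the third, and the only joint null hypothesis is that all three means are equal. The F test already covers that at 5%. If exactly one pair is truly equal, only one true null remains, and testing it at 5% is enough. The second hurdle then mainly costs power.

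With 15 patients per arm that cost matters to any reader who wants to know which treatments differ, and not merely that some difference exists.

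**Working it through.** **Inputs from the documents.** Three arms, 15 per arm, alpha 0.05, one-way ANOVA, Bonferroni over three pairs. Pooled error df = 45 − 3 = 42.

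**The plan's own figure.** The sample size rests on this: "Based on a power of 0.80 and an alpha value of 0.05". No effect size, SD, outcome or test is given, so 45 cannot be reproduced, only solved backwards. For a three-group F test, 80% power at N = 45 needs Cohen's f = 0.480.

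**Assumed effects.** If one arm differs by δ SD and the other two are equal, f = δ√2/3, so f = 0.48 gives δ = 0.48 × 3/1.414 = 1.02. If the arms are evenly spaced at −a, 0, +a, f = a√(2/3), so a = 0.48/0.816 = 0.588. Both are assumptions, chosen only because they match 80% omnibus power.

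**Thresholds.** The standard error of a pairwise difference is √(2/15) = 0.365 SD.

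- Pair at 0.05: |t| > 2.018, an observed difference of 2.018 × 0.365 = 0.74 SD.
- Pair at 0.0167: |t| > 2.494, an observed difference of 2.494 × 0.365 = 0.91 SD.

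Every pair rejected by the gated Bonferroni rule is also rejected by the closed test, so the change loses no finding.

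**Familywise error** (simulation, normal data, equal SDs, 400,000 trials per pattern):

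| True pattern | F, then pairs at 0.05 | F, then Bonferroni |
|---|---|---|
| All equal | 4.9% | 4.1% |
| One arm differs by 1.02 SD | 4.9% | 1.7% |
| One arm differs by 5 SD | 5.0% | 1.7% |

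The gate is essential: unadjusted pairs without it give 12.0% when all arms are equal.

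**Power, same simulation:**

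| True pattern | Bonferroni | Closed test |
|---|---|---|
| One arm differs by 1.02 SD, each true pair | 0.62 | 0.73 |
| Same, both true pairs found | 0.46 | 0.65 |
| One arm differs by 1.06 SD, each true pair | 0.66 | 0.76 |
| One arm differs by 2 SD, each true pair | 0.998 | above 0.999 |
| Evenly spaced, adjacent pairs | 0.20 | 0.34 |
| Evenly spaced, extreme pair | 0.76 | 0.79 |

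The gain is large for moderate differences, small for the widest pair of evenly spaced arms, and nil for very large effects. Holm, a simpler alternative, falls in between (0.65 per pair and 0.53 for both pairs at 1.02 SD).

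**Unequal SDs.** The documents give no SDs, so these are assumed. With SDs 1.5, 1.5 and 1, where the two equal arms have the larger SD, the pooled variance is (2.25 + 2.25 + 1)/3 = 1.83. The null pair's true variance is 2.25, so its t statistic is too large by √(2.25/1.83) = 1.11. Simulated error on that pair when the third arm is far away:

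| SDs | Closed, pooled error | Bonferroni, pooled error |
|---|---|---|
| 1.5, 1.5, 1 | 7.7% | 3.0% |
| 2, 2, 0.5 | 10.5% | 4.8% |

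With a Welch ANOVA followed by Welch t tests, the error is at most 5.0% in both cases. With equal SDs and a 1.02 SD difference, Welch gives 0.71 per true pair for the closed test and 0.59 for Bonferroni. Welch therefore costs about 2 points (0.73 to 0.71) and keeps the gain.

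**Comparisons at each time point.** The plan specifies no three-arm test at each visit. If the overall repeated-measures group effect were used as the gate, it could open because of one visit while the arms are equal at another. With arms differing only at T1 (assumed 6 SD, within-patient correlation 0.5), the error at a later null visit was 12.1% for unadjusted pairs and 4.2% with Bonferroni.

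**The case against.** The strongest reply is that nothing is broken. Bonferroni controls the familywise error within each ANOVA, matches simultaneous confidence intervals, and is robust. That stands: this is a point of efficiency. A reader might infer that the planned error control is faulty; the documents do not support that.

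A reader might also infer that the Bonferroni step buys nothing. That goes too far. The pain outcomes are a 0–10 rating and a 0–3 scale, both bounded at zero. If one treatment works well, its scores crowd towards zero and its SD shrinks, which is the pattern that inflates the pooled closed test. In simulations of such bounded scores with assumed means, the error on the remaining null pair was about 8%, against about 3.5% with Bonferroni. The margin protects when the error term is pooled. Welch tests supply that protection at a lower price.

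Finally, a reader might extend the argument to the second Bonferroni sentence. It does not carry over, because no same-visit omnibus test is planned and so no second hurdle is being paid for.

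Two smaller cautions also stand. The 1.02 SD difference is not the plan's figure. And the analysis text is in the past tense, so results may already have been seen.

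**Conclusion.** The point holds as a cheap, optional improvement to the one-way ANOVA sentence. At an assumed 1.02 SD difference in one arm, the closed test adds about 11 points of power per true pair and about 19 points for finding both, at 5% familywise error. Other patterns gain less: 3 points for the extreme pair of evenly spaced arms.

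The conclusion rests on exactly three arms, an omnibus gate for the same outcome and time point, and either roughly equal SDs or Welch tests. It covers one ANOVA only. Neither method deals with multiplicity across three outcomes (1 − 0.95³ = 14.3% if independent) or three outcomes by three follow-up visits (1 − 0.95⁹ = 37.0%).

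**What to change.** Replace the post hoc sentence with wording such as: *Within one outcome and time point, if the three-arm Welch ANOVA is significant at 0.05, each pair is tested at 0.05 with a Welch t test; if not, no pair is declared different.*

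For the comparisons at each time point, either add a three-arm test at that same visit as the gate, or leave Bonferroni (or Holm) in place. The overall repeated-measures group effect must not serve as the gate.

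The costs are a change of SAP wording, an added omnibus test per visit if the rule is extended there, and about 2 points of power for Welch when SDs are equal. The 95% confidence intervals would be unadjusted, not simultaneous, and should be labelled so. Multiplicity across outcomes and visits needs its own rule.

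If outcome data have already been analysed, keep Bonferroni as planned and report the closed test as a labelled sensitivity analysis, because moving to a more liberal rule after seeing results would be data-driven.

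### Repeated-measures ANOVA over visits that appear to include T0, without baseline adjustment or a rule for missed visits, is less efficient than a baseline-adjusted mixed model on T1–T3

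*Combined protocol and SAP*

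**What the plan says.** The combined protocol and SAP describes a randomised trial: "This is a 3-armed randomized, parallel, controlled, interventional clinical study enrolling 45 patients". Its Outcome measures section sets four assessments: "The patients were assessed before the injections (T0), and at one week (T1), 4 weeks (T2), and 12 weeks (T3) after the injections".

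The Statistical Analysis Plan paragraph in the same section gives the longitudinal method in one sentence: "Repeated Measures ANOVA test was used when testing group differences for repeated measurements". It adds: "Bonferroni correction was used in multiple comparisons when determining the differences between the groups at each time point". A one-way ANOVA of percentage change from baseline is planned separately.

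The paragraph does not say whether T0 is an outcome level or a covariate, or whether the group main effect or the group-by-time interaction is the test of treatment. It gives no sphericity check or correction and no rule for missed visits. The Sample size section gives power, alpha and N, with no effect size, SD, named test or allowance for loss.

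**The concern.** Randomisation gives the arms the same expectation at T0. If T0 is one of four levels of the time factor, a main effect averaged over all four mixes one time point that carries no treatment effect with three that may. The interaction avoids this, but it is a multi-degree-of-freedom test whose usual F reference depends on sphericity. Visits at 0, 1, 4 and 12 weeks make equal correlations unlikely.

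Neither term uses the baseline score as a covariate, although every patient has one. The classical procedure also analyses complete cases only. With 15 patients per arm, a few missed visits cost power. If missing a visit is related to recovery or failure, excluding those patients could bias the comparison at every time point.

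**Working it through.** **Inputs from the document.** Three randomised arms (Study Design); 45 patients, 15 per arm, power 0.80, alpha 0.05 (Sample size); one pre-treatment and three post-treatment visits (Outcome measures).

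**Assumptions.** T0 is a level of the time factor; the effect is constant over T1–T3; SDs are equal; the correlation r between any two visits is 0.3, 0.5 or 0.7.

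**1. The plan's own figure.** N = 45 cannot be reproduced, because no effect size, SD or test is stated. Solving backwards for a one-way ANOVA (df 2 and 42, non-centrality 45f²), 80% power corresponds to f = 0.4797, so 45 × 0.4797² = 10.36. This serves only as a scale for comparing methods.

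**2. Dilution of the group main effect.** The expected contrast is (0 + d1 + d2 + d3)/4 = 0.75 × (d1 + d2 + d3)/3. In units of its own SD the ratio is 0.75 × √(v3/v4), where v4 = (1 + 3r)/4 and v3 = (1 + 2r)/3 are the variances of the four-visit and three-visit means.

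| r | v4 | v3 | ratio |
|---|---|---|---|
| 0.3 | 0.475 | 0.533 | 0.795 |
| 0.5 | 0.625 | 0.667 | 0.775 |
| 0.7 | 0.775 | 0.800 | 0.762 |

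The standardised loss is therefore about 20–24%.

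**3. Power, from the noncentral F.** Non-centralities:
- main effect over T0–T3 (df 2, 42): 10.36 × 0.5625/v4 = 12.3, 9.3, 7.5
- group-by-time (df 6, 126): 10.36 × 0.75/(1 − r) = 11.1, 15.5, 25.9. The 0.75 is the sum of squares of (0, 1, 1, 1) about its mean.
- T1–T3 average, unadjusted (df 2, 42): 10.36/v3 = 19.4, 15.5, 12.9
- T1–T3 average, baseline-adjusted (df 2, 41): 10.36/(v3 − r²) = 23.4, 24.9, 33.4

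| r | Main effect, T0–T3 | Group-by-time | T1–T3, unadjusted | T1–T3, adjusted |
|---|---|---|---|---|
| 0.3 | 0.87 | 0.67 | 0.98 | 0.99 |
| 0.5 | 0.75 | 0.84 | 0.94 | 0.99 |
| 0.7 | 0.66 | 0.98 | 0.88 | above 0.99 |

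**4. Where the gain over the main effect comes from, as a multiple of patients.**
- Dropping T0 alone: v4/(0.5625 × v3) = 1.58, 1.67, 1.72.
- Adding baseline adjustment: v3/(v3 − r²) = 1.20, 1.60, 2.58.
- Both together: 1.9, 2.7, 4.4.

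**5. Sphericity.** In 20,000 simulated null trials per pattern, with 15 per arm, four visits and no correction, the type I error of group-by-time was:
- 5.1% under compound symmetry;
- 6.7% with correlation 0.7 per visit step;
- 8.1% with correlation 0.9 per week;
- 7.5% with correlation 0.7 per step and SDs rising from 1 to 2.

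Over all decaying-correlation patterns tried, the range was about 6–9%. The group main effect stayed at 4.7–5.2% throughout.

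**6. Complete cases.** With an assumed independent probability m of missing each follow-up visit, 45 × (1 − m)³ patients remain: 38.6 at m = 5% and 32.8 at m = 10%. One-way ANOVA power at f = 0.48 is 0.73 with 39 patients and 0.65 with 33.

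**The case against.** The plan never says that T0 is a level of the time factor; that is inferred from the visit list. When T0 is included, group-by-time is the usual test of treatment, and T0 acts as its reference without diluting it. At correlation 0.5 and 0.7 it has more power than the main effect. The planned comparisons at T1, T2 and T3 and the percentage-change ANOVA are not diluted either. A test at T0 is redundant but does not bias the later ones. A sphericity correction might be applied although none is written, and no dropout rate is given. If the same patients miss several visits, fewer are lost than under independence.

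All of this stands, and it limits what can be claimed. A reader might infer that the plan's group test is both diluted by 25% and dependent on sphericity. The document does not support that: the plan does not name the tested term, and no single term has both faults. The main effect is diluted but does not need sphericity; the interaction needs sphericity but is not diluted. Nor is 4.4 times the patients the price of including T0, since at correlation 0.7 most of that ratio comes from baseline adjustment.

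The objection does not make the planned procedure as good as the alternative. Either term has less power than the baseline-adjusted average in every constant-effect scenario above. The percentage-change ANOVA uses baseline only as a reference and does not adjust for it as a covariate.

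**Conclusion.** The concern holds as a loss of efficiency together with an underspecified analysis. If T0 is an outcome level, the main effect estimates 75% of the average post-treatment difference. If group-by-time is the test, the effect is spread over 6 degrees of freedom, and type I error is about 6–9% when correlation decays and no correction is made. In both cases a better use of data already collected is available: power of at least 0.99, against 0.66–0.87 for the main effect and 0.67–0.98 for the interaction.

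These sizes rest on a back-solved f of 0.48, a constant effect, equal SDs and assumed correlations. The type I range rests on assumed covariance patterns. A reader might also infer that a substantial share of patients will be lost; the document gives no loss rate, so the complete-case problem is a risk of unknown size. Confidence is medium.

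**What to change.** Replace the repeated-measures ANOVA with a linear mixed model:
- outcomes at T1, T2 and T3;
- fixed effects for arm, visit, arm-by-visit, T0 score and T0-by-visit;
- unstructured covariance;
- REML with Satterthwaite degrees of freedom, or Kenward–Roger where the software offers it;
- every available visit of every randomised patient, stating that missed visits are assumed missing at random given the observed data.

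Take the arm contrasts at each visit and averaged over visits from this model, and say in advance which of them is the main test. Drop significance tests at T0 and describe baseline instead.

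This settles T0's role, the tested term, the dependence on sphericity and the handling of missed visits together. It costs SAP wording and a change to another standard procedure, with no new data.

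### Three outcomes at three follow-ups are tested by two analyses at p < 0.05 with no primary named; Bonferroni covers only comparisons between arms, so 0.05 is not the error rate of the trial's conclusion

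*Combined protocol and SAP*

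**What the plan says.** All references are to the combined protocol and SAP.

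- **Outcomes and visits (Outcome measures).** Pain on function (NRS 0–10), pain on palpation (4-point scale) and pain-free mouth opening (mm) are listed side by side. They are taken at T0 and again at 1, 4 and 12 weeks: "Patient's pain on palpation, pain on function and maximum mouth opening values were reexamined and recorded on follow-up appointments". Neither an outcome nor a visit is called primary.
- **Analyses (Statistical Analysis Plan paragraph).** One-way ANOVA is used for change variables, with the percent difference from baseline to T1 given as an example. Repeated-measures ANOVA is used for group differences over the repeated measurements. Pearson chi-square is used for categorical variables.
- **Multiplicity.** Bonferroni is named as the post hoc test after ANOVA, and again for the per-visit comparisons: "Bonferroni correction was used in multiple comparisons when determining the differences between the groups at each time point".
- **Threshold.** "The statistical significance level was accepted as" p < 0.05, with no division of that level.
- **Sample size.** The stated inputs are 80% power and a 5% alpha, and the result is given as "the sample size was calculated to be a total of 45 subjects with 15 in each group". The section links this to no outcome, visit, test or effect size, so it does not identify a primary endpoint indirectly.

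**The concern.** With three arms there are three arm pairs, and Bonferroni over those pairs handles one source of multiplicity. Three others are left open: three outcomes, three follow-ups, and two inferential analyses of the same data. The overall ANOVA tests are also unadjusted.

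The plan does not say which of these tests decides whether the techniques differ. A reader of the results could not separate the test that was meant to answer the question from one that crossed 0.05 by chance. With 15 patients per arm, a reported difference between nerve block, local anesthetic injection and dry needling could rest on a single outcome at a single visit in one of the two analyses. The nominal 5% would not describe the risk that such a difference is false.

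**Working it through.** **Inputs from the documents.** 3 arms of 15 (N = 45); 3 outcomes; 3 follow-ups after T0; two analyses; 0.05 per test; Bonferroni over 3 arm pairs (0.05/3 = 0.0167 per pair).

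**Inputs not in the documents, assumed.** Correlation between visits 0.5–0.7; correlation between outcomes 0.3–0.7; normal data; a baseline spread for percent change (for example mean 6, SD 1.5, a coefficient of variation of 0.25).

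**The plan's own figures.** It states no familywise error rate, so there is none to reproduce. N = 45 cannot be reproduced either, because no effect size is given. Solving backwards for a one-way ANOVA with 3 groups, alpha 0.05, power 0.80 and N = 45 (noncentral F on 2 and 42 degrees of freedom, noncentrality N·f²) gives Cohen's f ≈ 0.48.

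**Step 1: count the tests.**
- Percent-change ANOVAs: 3 outcomes × 3 follow-ups = 9, if the baseline-to-T1 example extends to T2, T3 and all outcomes; 3 if only T1 is tested.
- Arm pairs at follow-up: 9 × 3 = 27, each Bonferroni-corrected by 3.
- Repeated-measures tests: group and group-by-time for each outcome, 3 × 2 = 6.

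**Step 2: reference values if tests were independent**, 1 − 0.95^m:
- m = 3: 1 − 0.95³ = 0.143
- m = 9: 1 − 0.95⁹ = 0.370

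**Step 3: allow for correlation.** Trials were simulated with no true difference (3 × 15 patients, 3 outcomes × 4 times), and those with at least one significant result were counted:

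| Reading of the plan | Chance of at least one significant result |
|---|---|
| Three T1 percent-change ANOVAs only | 11–14% |
| Arm pairs, only after a significant repeated-measures test | 11–15% |
| 27 arm pairs, not gated | 21–29% |
| Nine percent-change ANOVAs | 24–32% |
| Every test counted, not gated | 42–52% |

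The percent-change row depends on the assumed baseline spread; with mean 6 and SD 1.5, one run reached 34%. With both correlations at 0.9, the nine percent-change ANOVAs still give about 19%, and every test counted gives about 33%.

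**Step 4: effect of the correction.** One pre-specified test gives 5%. Bonferroni's threshold over nine tests, 0.05/9 = 0.0056, caps that family at 5%; under independence it gives 1 − (1 − 0.05/9)⁹ = 0.049. Holm has the same cap and the same first threshold.

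**Step 5: power cost of Holm.** At f ≈ 0.48 the noncentrality is 45 × 0.48² ≈ 10.4. The critical F rises from 3.22 (0.05) to 5.89 (0.0056), and power falls from 80% to about 49%. Regaining 80% at that threshold needs f ≈ 0.62.

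**The case against.** The best defence is that Bonferroni is already in the plan and that the larger percentages depend on a generous count. Much of this is fair:

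- Calling Bonferroni a post hoc test suggests that pairs are examined only after a significant overall test. Gating the pairs on a repeated-measures test roughly halves their error, from 21–29% to 11–15%.
- Only the baseline-to-T1 percent change is named. Extending it to T2, T3 and all outcomes is a natural reading, but not explicit text.
- The plan does not say which repeated-measures effect is tested, or whether the 4-point palpation score goes to ANOVA or chi-square.
- The documents make no confirmatory claim for this 45-patient comparison, so an exploratory label would be a legitimate answer.

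These points lower the figure but do not remove the defect. The narrowest readings above still give two to three times 5%. If the Bonferroni sentence were read as also spanning visits, the nine percent-change ANOVAs would remain unadjusted.

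Three stronger inferences are tempting and are not supported. The first is that any p < 0.05 counts as a positive trial: the plan states a significance level, but no success rule and no superiority claim. The second is one headline error rate for the plan: a single range running from the mid-twenties to about 50% would join one analysis at its lower end to the full list of tests at its upper end. The third is that the plan ignores multiplicity: it adjusts between arms, though nowhere else.

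**Conclusion.** The point holds. Three outcomes and three visits of equal standing are tested by two analyses at 0.05. Adjustment is confined to comparisons between arms, and no rule identifies the deciding result. That much is read directly from the text and needs no assumption.

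The size does need assumptions, namely the correlations, the baseline spread and the test list, and is best given by reading: 11–15% on the narrow readings, 24–32% for nine percent-change ANOVAs, 42–52% with every test counted and no gating. Every reading tried exceeds 5%. The rate would fall back towards 5% only if the outcomes carried almost the same information or most of the listed tests were not used for inference, and the plan says neither. Confidence is high in the structural defect and moderate in any particular percentage.

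**What to change.** **If outcome data have not been examined.** Name one primary outcome, time point and analysis. One example is PoF at T3: a three-arm omnibus test adjusted for T0 at 0.05, followed by Bonferroni-corrected pairs only if it is significant. Use one inferential analysis per outcome, and state which test applies to the 4-point palpation score. Label the remaining outcomes and visits secondary under Holm, or exploratory with no significance claim.

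**If outcome data have been examined.** The plan is written in the past tense, which leaves this open. In that case do not choose a primary now. Either apply Holm across the nine outcome-by-visit omnibus tests on a single stated scale (for example baseline-adjusted values rather than percent change), with the smallest p-value compared with 0.05/9 = 0.0056, or report all results as exploratory.

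**Cost.** SAP wording, and fewer results that can be called significant. Under Holm, an effect with 80% power at 0.05 has about 49% power at the first step, and 80% needs f ≈ 0.62 instead of 0.48. A single pre-specified primary avoids that loss; the exploratory label avoids it too, but gives up any significance claim.
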